### **Background, Rationale and Context**

Total hip arthroplasty (THA) remains one of the most successful orthopedic procedures in that it can effectively relieve pain and restore function in patients with end stage osteoarthritis. In an attempt to accelerate recovery, many orthopedic surgeons have opted to utilize a direct anterior approach (DAA) as opposed to the more traditional posterolateral approach (PLA). The literature supports that DAA is superior to PLA with regard to lower blood loss, less pain, shorter hospital stay, and faster rehabilitation. The DAA technique involves dissection of muscular planes for insertion of components resulting in less tissue damage as compared to PLA. For this reason, we are seeing more DAA total hip arthroplasty procedures performed at our institution.

Traditionally, we perform Lumbar Plexus blocks (LPB) in a manner consistent with that described by Capdevila et. al to provide post-operative analgesia for total hip arthroplasty. This technique works well for the traditionally performed PLA in that the hip joint and incision site are within the analgesic distribution of the LPB. Conversely, the DAA utilizes an anterior incision that overlies the L1 and L2 dermatomes as opposed to the lower lumbar dermatomes of the PLA incision. The incision runs proximal to distal starting 3cm distal to and 3cm lateral to the anterior superior iliac spine. When performing LPB, it has been our clinical experience that it is rare to achieve analgesia in the proximal distribution of the lumbar plexus resulting in apparent sparing of the L1 and L2 nerve root distributions.

The Quadratus Lumborum block (QLB) is a newer regional analgesic technique that may be as effective as LPB at providing pain control following DAA hip arthroplasty. The QLB as described by Børglum is thought to provide analgesia by blocking both the lateral and anterior cutaneous branches of T7 through L4. This degree of dermatomal coverage suggests that QLB could be an efficacious alternative to LPB for DAA hip arthroplasty. To the best of the authors' knowledge, there has been no investigation comparing the efficacy, with regards to post-operative pain management, between LPB and QLB.

Analgesic modalities commonly employ primarily opioid therapy, however there is increased attention in the literature that supports minimizing opioid related adverse effects using multimodal analgesic therapies and avoiding an increase in the use of known agents that contribute substantially to adverse effects, including post-operative nausea and vomiting, hypoxia, and urinary retention. In contrast, analgesia provided by regional anesthesia results in a decreased risk of the aforementioned complications. It is therefore postulated that, at minimum, analgesic efficacy would be comparable, and potentially improved for DAA procedures through the use of a QLB versus LPB.

In order to compare a QLB to a LPB, we must first assess patient pain scores 6 hours after receiving a LPB and spinal anesthetic (both are considered a practice standard for our institution) for DAA procedures. We also want to test the presence or absence of pin prick sensation at the base of the 1st toe (L5 dermatome) and the base of the 5th toe (S1 dermatome) 6 hours postoperatively. This will allow us to assess for spinal resolution below the level of the lumbar plexus. Intact sensation at L5 and/or S1 in addition to a demonstrable lumbar plexus block would indicate that the pain scores obtained at 6hrs would represent analgesia provided by the lumbar plexus block alone.

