## **Objectives**

The purpose of this study is to collect pilot data to help the design of a future randomized study, comparing a QLB to a LPB for DAA procedures. We will collect pain scores measured on a visual analog scale at 6hrs. Additionally, we will assess for spinal resolution below the level of L5/S1 by assessing the presence of absence of pin prick sensation at these levels. This will help determine if pain scores collected at 6hrs reflect analgesia provided by the preoperative LPB alone or if the data is confounded by the presence of spinal anesthesia. This data will help us determine if 6hrs is a feasible primary endpoint to assess pain scores. Additionally, assuming that spinal regression is complete by 6hrs, the VAS pain scores obtained will then be used to perform a power analysis to determine the necessary study size when comparing QLB to LPB for DAA hip arthroplasty.

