## **Methods**

Study staff will visit 10 patients, at their hospital rooms, 6 hours after a LPB and spinal block are performed for their DAA hip surgeries. Patients will be asked to verbally rate their pain, on a scale from 0 to 10, when resting and when they sit up in bed. Study staff will use a blunt needle to touch the base of the 1st toe (L5) and the base of the 5th toe (S1), without breaking the skin. Patients will be asked if they can feel “pinprick,” touch, pressure, or nothing.

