## **Outcomes:**

Outcomes will include patient pain scores (rest and with activity) and the presence or absence of pin prick sensation 6 hours post LPB placement.

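### Could the pinprick check fall hours after the pain score it is meant to validate, because the Background counts 6 hours from a different start?

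*Protocol*

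**What the plan says.** The Protocol mentions the 6-hour assessment in four sections.

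- **Background, Rationale and Context, last paragraph.** For pain: "we must first assess patient pain scores 6 hours after receiving a LPB and spinal anesthetic". The next sentence, on sensation at the two toe sites, ends with "toe (S1 dermatome) 6 hours postoperatively". The paragraph then gives the purpose of the test: intact L5 and/or S1 sensation, together with a demonstrable LPB, "would indicate that the pain scores obtained at 6hrs would represent analgesia provided by the lumbar plexus block alone".
- **Objectives.** "We will collect pain scores measured on a visual analog scale at 6hrs", with no start named for the 6 hours. The same section asks whether the scores "reflect analgesia provided by the preoperative LPB alone", which confirms that the block precedes surgery.
- **Methods.** Staff visit 10 patients in their rooms "6 hours after a LPB and spinal block are performed for their DAA hip surgeries". Under that visit come first the pain rating ("Patients will be asked to verbally rate their pain, on a scale from 0 to 10", at rest and on sitting up) and then the blunt-needle test at the two toes.
- **Outcomes.** One sentence covers the pain scores and "the presence or absence of pin prick sensation 6 hours post LPB placement".

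**The concern.** Two consecutive sentences of the Background use different clocks. A preoperative block and a postoperative origin cannot share a zero time. Taken literally, pain is scored 6 hours after the block, and sensation is tested later by however long the patient takes to get from block to end of surgery.

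That would matter here because time since the spinal is what the pilot studies. The pinprick result decides whether a pain score can be credited to the LPB alone, and that inference needs both measurements at the same time since the spinal. A later sensory test errs in one direction. It gives the spinal longer to regress, so a pain score taken under residual spinal anesthesia could be accepted as LPB analgesia.

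Both products of the pilot would be affected: the judgment on whether 6 hours is a workable primary endpoint, and the pain scores passed to the power analysis for the future randomized study. If staff mixed the two clocks, 10 patients would be pooled over different times since the spinal.

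**Working it through.** The Protocol states no figure to reproduce. The check is to set the time origins side by side and ask which schedule the operative text produces.

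| Section | Pain score counted from | Pinprick counted from |
|---|---|---|
| Background | LPB and spinal | postoperative |
| Objectives | not stated | not stated |
| Methods | LPB and spinal (one visit) | LPB and spinal (same visit) |
| Outcomes | LPB placement | LPB placement |

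Only one of these entries uses a postoperative origin. Every other entry that names an origin uses the block.

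**Literal Background reading.** Let *d* be the interval from block to end of surgery. The Protocol does not give *d*, and taking the postoperative clock to start at the end of surgery is itself an interpretation.

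- Pain score: 6 h after the block.
- Pinprick: 6 + *d* h after the block.
- Gap: (6 + *d*) − 6 = *d*.

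Assume for illustration that *d* runs from 1.5 to 3 h:

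- Pinprick falls at 6 + 1.5 = 7.5 h to 6 + 3 = 9 h after the block.
- Extra time for the spinal to regress is 1.5/6 = 25% to 3/6 = 50%.
- The pain score falls at 6 − 3 = 3 h to 6 − 1.5 = 4.5 h after surgery.

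With *d* = 1 h, the gap is 1 h, or 1/6 ≈ 17%. The direction is the same for any positive *d*.

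**Methods and Outcomes reading.** Pain score and pinprick are both at 6 h after the block, at one visit. Gap: 6 − 6 = 0 h, apart from the minutes needed to do one after the other.

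**Which reading governs.** Methods tells staff what to do and when. It describes one visit, and no section describes a second. The Background passage explains why the test is wanted, and its closing inference treats pain and sensation as belonging to a single 6-hour time point. To split the two measures, staff would have to follow Methods for pain and a word of the rationale for pinprick.

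**If staff used the wrong clock throughout.** The single visit would move to 6 + *d* h after the block, but pain and sensation would still be taken together. The pinprick result would still describe the spinal at the time of the pain score. That would be a departure from Methods, not something the plan prescribes.

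**The case for a change.** The strongest case for acting starts from the fact that 6 hours is the study's only time point, and everything it delivers depends on where those hours start. Objectives, the section that states the deliverable, names no start. With 10 patients, a few visits on the wrong clock would noticeably shift both the proportion with a resolved spinal and the spread of pain scores. The Confidentiality and Privacy section limits the data to pain scores and sensation, so no elapsed time is recorded and a mistimed visit could not be found afterwards. Designers of the next trial might also take their endpoint from the Background and adopt a time point that the pilot never tested. Aligning one word would cost almost nothing.

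Part of this stands. The wording is inconsistent, Objectives is silent on the origin, and the data set could not reveal a mistimed visit. But each harm requires someone to set aside Methods, which gives one clock and one visit, and Outcomes, which agrees with it. A reader of Objectives finds the missing origin in either section.

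The suggested remedies add little. A statement that both measures are taken at one visit would repeat Methods. Recording minutes from block and from end of surgery would be new data on each patient, and it is not needed to settle the wording. It would also conflict with the Confidentiality and Privacy section. The Informed Consent section rests the absence of consent partly on collecting no patient information, a limit wider than identifiers alone. Those sections would have to be reopened to guard against a deviation that the plan does not invite.

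**Conclusion.** The concern does not call for a change. There is a one-word slip in the rationale: the postoperative origin for pinprick disagrees with the pain-score sentence before it, with Methods and with Outcomes. The feared consequence, a sensory test hours after the pain score, does not follow from the plan, because the operative sections put both measures at one visit 6 hours after the block. The planned gap is about 0 h.

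The 7.5 to 9 h timing, and the 25% to 50% of extra regression time, describe a schedule that Methods does not prescribe. They depend on an assumed interval of 1.5 to 3 h.

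The conclusion assumes that staff work from Methods and that the results are read against the time point in Outcomes. On that basis, correcting the word would be a tidy-up with no effect on what is measured, when it is measured, or what can be concluded about 6 hours as an endpoint.

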## **Objectives**

The purpose of this study is to collect pilot data to help the design of a future randomized study, comparing a QLB to a LPB for DAA procedures. We will collect pain scores measured on a visual analog scale at 6hrs. Additionally, we will assess for spinal resolution below the level of L5/S1 by assessing the presence of absence of pin prick sensation at these levels. This will help determine if pain scores collected at 6hrs reflect analgesia provided by the preoperative LPB alone or if the data is confounded by the presence of spinal anesthesia. This data will help us determine if 6hrs is a feasible primary endpoint to assess pain scores. Additionally, assuming that spinal regression is complete by 6hrs, the VAS pain scores obtained will then be used to perform a power analysis to determine the necessary study size when comparing QLB to LPB for DAA hip arthroplasty.

## **Methods**

Study staff will visit 10 patients, at their hospital rooms, 6 hours after a LPB and spinal block are performed for their DAA hip surgeries. Patients will be asked to verbally rate their pain, on a scale from 0 to 10, when resting and when they sit up in bed. Study staff will use a blunt needle to touch the base of the 1st toe (L5) and the base of the 5th toe (S1), without breaking the skin. Patients will be asked if they can feel “pinprick,” touch, pressure, or nothing.

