## **Interventions**

Interventions are limited to a pin prick sensation testing at the base of the 1st toe and of the 5th toe.

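### The protocol does not fix or record which foot is pinprick-tested, and no listed assessment shows the working lumbar plexus block that its own attribution rule requires

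*Protocol*

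**What the plan says.** The Methods section sets the sample and the time: "Study staff will visit 10 patients, at their hospital rooms, 6 hours after a LPB and spinal block are performed for their DAA hip surgeries". It then describes the sensory test: "Study staff will use a blunt needle to touch the base of the" first toe (L5) and the fifth toe (S1). No foot is named.

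The Background section explains the choice of sites: "This will allow us to assess for spinal resolution below the level of the lumbar plexus". It then gives the rule for reading the result: "Intact sensation at L5 and/or S1 in addition to a demonstrable lumbar plexus block would indicate that the pain scores obtained at 6hrs would represent" the effect of the LPB alone. The rule has two conditions: sensation at one or both toe sites, and a block that can be shown to be present.

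The Objectives section rests the pilot on this reading: "This will help determine if pain scores collected at 6hrs reflect analgesia provided by the preoperative LPB alone or if the data is confounded by" residual spinal anesthesia. The answer bears on whether 6 hours is a usable primary endpoint and whether the scores go into the power analysis for the randomized trial.

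The Interventions section confines testing to the toes ("Interventions are limited to a pin prick sensation testing at the base of the" first and fifth toes). The Outcomes section reads: "Outcomes will include patient pain scores (rest and with activity) and the presence or absence of pin prick sensation 6 hours post LPB placement". Confidentiality and Privacy restricts the data to pain scores and whether sensation is present. None of these sections mentions the side tested or a test of the block.

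**The concern.** The pilot has to separate two sources of analgesia at 6 hours. I assume that the LPB is placed for the operated hip only and that the spinal acts on both legs. The protocol does not state this, but comparing the legs depends on it.

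Two gaps follow. First, with the side neither fixed nor recorded, a missing toe response has no settled meaning, and the side cannot be recovered afterwards. On the operated foot it may reflect residual spinal or a block that has spread to L5/S1. Second, the attribution rule needs evidence that the block is working, and none is collected. A patient with intact toes and a failed block would look the same in the data as a patient with intact toes and a good block.

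At stake is the statement that the pilot exists to make: that the 6-hour scores reflect the LPB and nothing else. Both gaps concern a bedside procedure, which a protocol would not normally leave to an analysis plan.

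**Working it through.** **Step 1. Set the sections side by side.**

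| Protocol section | Toe sites | Side | Test of the block |
|---|---|---|---|
| Background | L5 and S1 | not stated | required by the rule, not described |
| Objectives | L5/S1 | not stated | none |
| Methods | 1st and 5th toe | not stated | none |
| Interventions | 1st and 5th toe only | not stated | none |
| Outcomes | present or absent | not stated | none |
| Confidentiality and Privacy | present or absent | not listed | not listed |

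**Step 2. Write the rule as logic.** Let A mean that L5 or S1, or both, are intact, and B that the block is demonstrable. The score is attributed to the LPB alone if A and B both hold. A is observed. B is not observed in any patient. The number of patients in whom A and B can be confirmed is therefore 0 of 10, even if A holds in all ten.

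**Step 3. Ask what one foot can show.** Take a foot as intact if at least one of its two sites is intact, in line with the and/or in the rule. Two feet give four states:

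| Operated foot | Other foot | Reading |
|---|---|---|
| intact | intact | spinal regressed |
| intact | lost | spinal regressed on the operated side |
| lost | lost | residual spinal |
| lost | intact | block spread or unequal regression: indeterminate |

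If only the operated foot is tested, the last two rows merge. If only the other foot is tested, rows 1 and 4 merge, and so do rows 2 and 3. If the side is not recorded, nobody can say which rows have merged. Intact sensation still shows regression at the site touched, on whichever foot it is found.

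**Step 4. Size.** With n = 10, one patient is 1/10 = 10 percentage points of the resolved proportion. Exact 95% (Clopper-Pearson) limits, which for 10/10 have the lower bound 0.025^(1/10) = 0.692:

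- 10/10: 69.2% to 100%
- 9/10: 55.5% to 99.7%
- 8/10: 44.4% to 97.5%

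These show how coarse the estimate is. They do not say how often a response would be misread, because the documents give no rate. The protocol states no alpha, power or precision for the ten patients, so there is no figure to reproduce.

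**The case against.** The strongest reply is that the protocol already separates spinal from block by level. The toe sites were chosen because they lie below the lumbar plexus, one intact site is enough, and patients with neuropathy of the feet are excluded. A misread response needs loss at both sites from something other than the spinal, and no document suggests how often that happens. The error would also be conservative: it would set aside a clean score, not pass a confounded one.

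Most of this stands, and it limits the side issue to one branch. The control by level is not fully secure at L5, however. Background places the posterolateral incision in the lower lumbar dermatomes and within the reach of the LPB, and reports sparing at L1 and L2. That does not say that the block reaches L5, but it does not rule it out.

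A second reply is that patients who do not receive an LPB are excluded. That ensures that a block was given, not that it worked, and the rule asks for the latter.

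Three stronger readings are tempting but unsupported:

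- **That the protocol leaves out the non-operated leg.** It is silent on side, and its wording fits one foot, the other or both.
- **That the other leg is the only available control.** Level is a control too.
- **That one or two misread patients would reverse the feasibility answer.** Objectives sets no threshold, and the intervals in Step 4 overlap heavily.

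**Conclusion.** The point holds in two parts.

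The missing block check is the firmer one. It follows from the text alone, and it means that the written rule cannot be met from the listed data in any of the ten patients.

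The unspecified side is narrower. It leaves absent responses uninterpretable if only the operated foot is tested, and leaves every response without a known side. It rests on the assumption that the LPB is one-sided and the spinal two-sided. Its frequency is unknown.

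No sample size or error rate in the protocol changes.

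A reader might infer that resolution should simply be judged on the non-operated foot. That would be unsound. The pain score comes from the operated hip, and such a rule assumes equal regression on both sides, which the protocol does not state. If regression were unequal, a confounded score could pass as clean. The two feet have to be read together.

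**What to change.** **Toes.** In Methods, Interventions and Outcomes, state that both toe sites are tested on both feet, and record each as operated or non-operated side. Define the reading in advance:

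- operated foot intact: spinal resolved;
- loss on both feet: residual spinal;
- loss on the operated foot only: indeterminate, counted and reported separately.

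**Block.** Add the same pinprick check on both thighs at a named lumbar plexus dermatome. Loss on the operated side with sensation on the other demonstrates the block. Loss on both thighs cannot separate block from spinal and should be reported as such. Because Background describes frequent sparing of L1 and L2, the named site should not be one where a working block is expected to miss.

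**Reporting.** Use the block check to label scores. Say separately whether patients without a demonstrated block stay in the power calculation.

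**Cost.** About one extra bedside minute per patient at a visit already planned, with matching edits to Methods, Interventions, Outcomes, and Confidentiality and Privacy. Interventions must change because it now limits testing to the toes. Recording operated or non-operated side adds no patient identifier. Treatment is unaffected.

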## **Setting**

All participating patients will receive their surgeries at Davie Medical Center of Wake Forest Baptist Health.

## **Subject Selection**

### **Inclusion**

Patients will be eligible for inclusion in the study if they are at or over the age of 18 years old and have elective total hip arthroplasty with DAA at Davie Medical Center.

### **Exclusion**

Patients will be excluded if they do not receive a lumbar plexus block and spinal anesthesia and/or if they have peripheral neuropathy affecting their feet.

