### **Confidentiality and Privacy**

The only information taken for this study will be pain scores and presence or absence of sensation. No patient identification numbers or characteristics will be collected. Patients will be referred to by a simple number (numbers 1 through 10).

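### The exclusion covers only peripheral neuropathy of the feet and there is no pre-block toe reading, so a pre-existing L5/S1 deficit of another cause could be read as an unresolved spinal

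*Protocol*

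**What the plan says.** **Eligibility.** The Inclusion section admits patients "at or over the age of 18 years old and have elective total hip arthroplasty with DAA at Davie Medical Center" and has no neurological criterion. The Exclusion section removes those who do not receive both blocks and those for whom the following holds: "if they have peripheral neuropathy affecting their feet". No other pre-existing sensory loss is named.

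**Measurement.** The Methods section states: "Study staff will visit 10 patients, at their hospital rooms, 6 hours after a LPB and spinal block are performed". The Outcomes section likewise gives a single sensory reading: "the presence or absence of pin prick sensation 6 hours post LPB placement". No reading before the block is described. The Confidentiality and Privacy section limits the record: "The only information taken for this study will be pain scores and presence or absence of sensation".

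**Use.** The Background says of the toe test: "This will allow us to assess for spinal resolution below the level of the lumbar plexus". Its rule begins: "Intact sensation at L5 and/or S1 in addition to a demonstrable lumbar plexus block would indicate that the pain scores". The Objectives section then states: "This data will help us determine if 6hrs is a feasible primary endpoint to assess pain scores". It also makes use of the pain scores in the later power analysis conditional on the spinal having fully regressed by that time.

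**The concern.** The toe test is defined by dermatome, whereas the exclusion is defined by one diagnosis. Excluding neuropathy of the feet shows that the plan recognises the threat: absent toe sensation that has nothing to do with the spinal spoils the test. Loss at L5/S1 from a nerve-root problem, earlier spine surgery or a central cause can produce the same reading and is not covered.

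Screening at entry is the only safeguard. Without a pre-block reading there is nothing to compare the 6-hour result with, and without recorded history an affected patient cannot be recognised afterwards. The patient's usual state could then be counted as residual anaesthesia, in a sample of ten whose purpose is to say whether 6 hours is a usable endpoint.

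**Working it through.** The Protocol gives ten patients without a calculation, so there is no planned figure to reproduce. The check is a reading of the text, followed by arithmetic for scale.

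**Inputs**
- n = 10 (Methods).
- One reading at 6 hours (Methods; Outcomes).
- Resolution rule: intact at L5 and/or S1 (Background).
- q, the share of enrolled patients with an L5/S1 deficit outside the exclusion: not in the documents, so assumed at 2%, 5% and 10%.
- s, the share of those deficits that affect both levels: not in the documents, so varied from 0 to 1.
- Patients are taken as independent.

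**Step 1. Can such a patient enter and go unnoticed?** Yes. Neither Inclusion nor Exclusion stops entry, no baseline reading exists, and no history is recorded.

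**Step 2. Is the patient then misread?** This depends on how the and/or rule is applied. The following assumes that the spinal has in fact resolved and that the deficit abolishes pinprick at the tested site.

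| Deficit | One intact level is enough | Both levels must be intact |
|---|---|---|
| One level only | Counted as resolved | Misread as unresolved |
| Both levels | Misread as unresolved | Misread as unresolved |

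**Step 3. Chance of including at least one affected patient:** 1 − (1 − q)^10.
- q = 2%: 1 − 0.98^10 = 0.183
- q = 5%: 1 − 0.95^10 = 0.401
- q = 10%: 1 − 0.90^10 = 0.651

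**Step 4. Chance of at least one misread.** If both levels must be intact, every affected patient counts, and the figures are those of Step 3. If one intact level is enough, only deficits at both levels count: 1 − (1 − q·s)^10. At q = 10%:
- s = 1: 1 − 0.90^10 = 0.651
- s = 0.5: 1 − 0.95^10 = 0.401
- s = 0.25: 1 − 0.975^10 = 0.224
- s = 0: 0

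Step 3 is therefore an upper bound on the chance of a misread.

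**Step 5. Effect of one misread patient.** The observed resolved share falls by 1/10, or 10 percentage points. If all ten had truly resolved, 10/10 (exact 95% interval 69% to 100%) would be recorded as 9/10 (56% to 99.7%). The shift always lowers the resolved share and so counts against 6 hours.

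**The case against.** The strongest objection is that the text supports a possibility only. Three stronger readings are tempting, and the documents support none of them.

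- **Any L5 or S1 deficit would be read as an unresolved spinal.** The Background accepts intact sensation at either level on one reading of its rule, so a patient with loss at one level can still count as resolved. The Methods section also records graded answers (pinprick, touch, pressure or nothing), and a deficit need not be complete. The foot to be tested is not stated, so a one-sided deficit may lie away from the test site.
- **The 18% to 65% is the chance of a wrong reading.** It is the chance of including an affected patient, at a prevalence that the documents do not give. The chance of a misread can be much lower, down to zero if one intact level is enough and no deficit affects both levels.
- **One such patient overturns the answer on 6 hours.** The Objectives section says only that the data will help with the decision. It sets no threshold and does not require all ten patients to pass. The intervals for 10/10 and 9/10 overlap widely.

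It can also be said that the error is cautious: it makes 6 hours look worse and does not pass off spinal analgesia as block analgesia. That is correct, but a bias against 6 hours is still an error on the question that the pilot asks.

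These points limit the consequence. They do not remove the gap, because the exclusion is narrower than the measurement and nothing later in the plan would reveal an affected patient. The and/or wording does not close it either, because the Protocol does not settle whether one level or both must be intact.

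**Conclusion.** The point holds as a design gap of modest and uncertain size. A pre-existing L5/S1 deficit from a cause other than peripheral neuropathy could be read at 6 hours as residual spinal. Given a deficit that abolishes pinprick at the tested site, this is certain only if both levels are affected or if the rule requires both to be intact.

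The 10-point shift per misread patient follows from the ten patients alone. How often it happens rests on the assumed 2% to 10% prevalence, on independence between patients, and on an unsettled rule, so 18% to 65% should be quoted only as an upper bound. The documents show no contradiction here. What is at issue is an exclusion that can be matched to its measurement at little cost.

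**What to change.** Reword the sensory part of the Exclusion section so that it follows the test sites and not one diagnosis, for example: *patients with any known pre-existing reduced sensation at the base of the first or fifth toe (L5 or S1), whatever its cause*.

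**Cost.** One line changes and a few patients are passed over, which slightly slows the recruitment of ten. The change relies on the same kind of screening as the present neuropathy exclusion and adds nothing to the data recorded, so the Confidentiality and Privacy section can stand.

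**What it leaves open.** Only known deficits are removed, so an unrecognised one could still be misread. A pinprick reading at the same sites before the block would catch those too, but it adds a patient contact and a data item that the plan does not now include. The rewording also does not settle the and/or rule in the Background.
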